Data Security. Ensuring data security, compliance with 45 CFR 46 and maintaining the integrity of PHI is a top priority. MUSC has Standard Operating Procedures (SOP) to ensure a high level of data security while coordinating electronic and paper data management activities for clinical research trials. The REDCap study database will be hosted in the Biomedical Informatics secure data center at MUSC, a secure environment for data systems and servers on campus, and includes firewall, redundancy, failover capability, backups and extensive security checks. The secure data center has strict access control; only authorized core personnel may access the facility un-escorted. Only authorized users are allowed to connect to the network, and the security of the network is actively monitored. Power and environmental controls have several layers of backups, from uninterruptible power supplies to alternate and redundant feeds to the local utility company. The REDCap system administrator contributes to the maintenance of institutional disaster recovery and business continuity plans. Load balancers and a highly fault tolerant SAN infrastructure contribute to high availability.

The REDCap system itself has several additional layers of protection including password protection. Access to the data and its security is managed institutionally by sponsored login IDs through a Shibboleth login with an MUSC issued NetID and features a user account management filter that controls who can access the data and to what degree. All personnel must pass an employment background check before being issued an ID. Password complexity, history and expiration standards are implemented at the institutional level. Access to individual REDCap projects and their data is managed by the owner of the project. All transactions are securely delivered to the application using Secure Sockets Layer (SSL – SHA-1 with RSA Encryption; 2048-bits). It is then transmitted internally (behind the firewall) to the database server. All transactions are logged at the server layer (httpd logging), application layers (REDCap logs activity to a database table), and the database layer, using both query and binary logging. This feature provides audit trails for all changes, queries, data exports and reports. MUSC Information security policies are available at: <https://mainweb-v.musc.edu/security/policy/>

Data Entry. Only MUSC IRB approved study personnel that are authorized to have access to the REDCap study database will be granted password access. Study personnel using computers that are connected to the Internet will directly enter data into the remotely housed database. As such, no electronic study data will be stored on hard drives and/or any portable electronic devices. Additionally, all personnel with access to the database will have current University of Miami CITI training in the

Conduct of Human Subject Protections, and their respective institution's HIPAA and Information Security trainings that are completed annually. Each participant will be assigned a unique study identifier, all PHIs will be masked, and data exports will be limited to the PI, the PD and the BS for generating reports and the conduct of statistical data analysis.

Data Monitoring. Ongoing quality control procedures will be implemented for data collection, storage and processing. The PD will conduct monthly monitoring of the study database and generate a report for the PI to review at team meetings. Standing agenda items for these meetings will include participant recruitment and retention, AE's, protocol deviations, data integrity and overall study conduct. The PD will work to resolve and validate discrepant data. Discrepancies that warrant clarification will be sent to appropriate parties for review and resolution. All data entry and changes made in the study database by authorized study personnel will be automatically logged by REDCap, and provide a transparent visible audit trail for reviewers.

SECTION C.

Procedures for Identifying, Reviewing and Reporting Adverse Events

1) Identifying. Potential minimum risks identified for participants are outlined in the Protection of Human Participants and will also be outlined in the IRB-approved informed consent document. Additional unknown risks may occur and, if so, will be identified through diligent monitoring by the PD and the frontline research team throughout the conduct of this study. During the informed consent process, participants will be advised of the potential minimum risks of participation as identified in the IRB-approved informed consent document and reminded throughout the study that the researchers should be promptly informed about any concerns regarding potential side effects, adverse events, or clinical deterioration. Participants will also be instructed to immediately notify the PI and/or designee of any suspected adverse events, if possible. Throughout the course of study, at each study contact, the researchers will elicit information about experienced AEs and monitor participant progress. The PD will maintain an electronic record of all reported adverse events and notify the PI and GE of all reportable events as they occur. The PD will generate and provide de-identified semi-annual administrative human participant safety reports for the SMC to review participant progress, accrual and attrition rates. Additionally, the BS will generate semi-annual safety reports for the SMC to provide for the monitoring of the frequency of all reported side effects and AEs.

2) Reviewing. Adverse events will be assessed and evaluated by the members of the SMC according to the following MUSC's IRB Adverse Event Reporting Policy

[http://academicdepartments.musc.edu/research/ori/irb/HRPP/HRPP%20Guide%20Section%204.7:](http://academicdepartments.musc.edu/research/ori/irb/HRPP/HRPP%20Guide%20Section%204.7)

- Expected/Anticipated—Identified in nature, severity, or frequency in the current protocol, informed consent, investigator brochure, or with other current risk information.
- Unexpected/Unanticipated—Not identified in nature, severity, or frequency in the current protocol, informed consent, investigator brochure, or with other current risk information.
- More Prevalent—Occurs more frequently than anticipated or at a higher prevalence than expected.
- Serious—Results in death, is life threatening, requires inpatient hospitalization or prolongs existing hospitalization, results in persistent or significant disability/incapacity, cancer, overdose, or causes a congenital anomaly/birth defect.

The relationship of adverse events to study participation will be determined by the DSMC according to the MUSC IRB Adverse Event Reporting Policy:

- Unrelated—There is not a reasonable possibility that the adverse event may have been caused by the drug, device or intervention.

- Possibly Related—The adverse event may have been caused by the drug, device, or intervention, however there is insufficient information to determine the likelihood of this possibility.
- Related—There is a reasonable possibility that the adverse event may have been caused by the drug, device or intervention.

3) Reporting. All reportable AE, SAE and unanticipated problems experienced by participants will be reported to the NIH/NINR and MUSC IRB in compliance with their Adverse Event Reporting Policy requirements, using the IRB's password protected on-line secure server adverse event reporting system. Within 24 hours after a reportable AE, SAE or unanticipated problem has been reported by the participant, it will be initially graded by the PD, forwarded to the study's C for review and approval, and then will be submitted by the PI to MUSC IRB. The Institutional Official(s) will review the event and discuss the report with the IRB Chair and the Director of the Office of Research Integrity. After IRB review and acknowledgement, the PI will further review, and the PD will forward a copy of the reportable AE, SAE or unanticipated problem and IRB acknowledgement letter to the NIH/NINR Program Officer through MUSC's OSRP. The activities will be reported to the NIH/NINR within 72hrs. In addition, all cumulative reportable AE, SAE and unanticipated problems included in the ISM reports will be submitted to the NIH/NINR in the PI's Annual Progress Reports.

4) Examples of Potential Reportable Adverse Events: In accordance with MUSC IRB Adverse Event Reporting Policy, an AE is reportable if it meets all of the following criteria: 1) is unexpected 2) is related and/or possibly related, and 3) is serious and/or suggests that the research places participants or others at a greater risk of physical or psychological harm than was previously known or recognized. Additionally, per MUSC's policy all participant deaths, protocol deviations, complaints about the research, and breaches of confidentiality are reportable events. From our previous work among this study population, an **example of an AE** would be feeling lightheaded or dizziness while or after performing the yoga breathing exercises. Depending on the severity, the possible steps to be taken include referral to a medical provider, resting in a prone position until the feeling subsides, and/or withdrawing the participant from the study. An **example of an SAE** would be the death of a participant from renal failure, which although would be viewed as unexpected and unrelated to the intervention is nonetheless a reportable serious event. No further steps would be taken except to review, grade and report the event to all applicable agencies. An **example of an unanticipated problem** would be the participant strains his or her neck while performing the yoga breathing. The steps in this case would be to withdraw the participant from the study and invite him or her to restart the study after the strain has resolved. These events and problems will be reported in accordance with the IRB and NIH/NINR policy as noted in Section C.3.

SECTION D. Multi-site Monitoring and Compliance

This is not a multi-site study.

SECTION E. Assessment of External Factors

The PI will conduct a semi-annual assessment of external factors through a review of literature related to new developments in the areas of yoga breathing among older populations, and other approaches that may have an impact on the safety of participants or on the ethics of the study. To determine whether any changes are necessitated to the study protocol, the SMC will review any identified literature or product safety data that may pose as a potential impact to the risk benefit ratio study and/or safety of study participants.

SECTION F. Interim Analysis

Based upon our prior research in this field among this same population and the minimal risk associated with the intervention, there are no stopping rules for this study. Accordingly, interim futility analysis will not be performed. However, the BS and PD will generate semi-annual qualitative interim analysis reports on a) adverse events; and b) data obtained during phone calls and returned end-of-study surveys to understand issues related to the uptake, usability, and adoption of the yoga breathing exercises among this population. We will also evaluate the screening and enrollment procedures, barriers to participation and retention, including, safety, adherence, acceptability, and feedback from the participants.

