4.0 Study Endpoints (all ARMS)

Study end points include: Successful study completion, participant consent withdrawal, and PI termination due to failure to adhere to the protocol, loss of contact with the patient, and/or unexpected adverse events.

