5.0 Inclusion and Exclusion Criteria/ Study Population

Inclusion criteria for ARMS 1, 2, and 3 are as follows:

- Males and females 60 years of age and older living in a Humanities Foundation apartment complex, HUD funded housing or living at 150% of poverty level
- PROMIS pain interference score of eight or above and/or a PROMIS pain behavior score of 15 or above
- Able to ambulate 150 feet with or without the use of an assistive device
- Able to follow simple instructions
- Able to read, speak, and write English,
- Able to operate tablet device and wearable activity tracker,
- Not currently enrolled in an exercise program.

Exclusion criteria for ARMS 1, 2, and 3 are:

- Inability or unwillingness of participant to give informed consent,
- Physical, cognitive, sensory or psychiatric disability that would limit participants from engaging in self-management program as noted by a Mini-Cog²⁶ score of 0-2.
- Unwillingness to wear a physical activity tracker during the course of the study.

Inclusion criteria for Supplemental ARM 4 are:

- CG must be able to speak and read English
- CG must be 45 years of age or older
- CG must be able to provide consent for themselves
- CG must live with or on same property as the PWD
- CG be primarily responsible for care provision of the PWD in the home (i.e., is not paid for services; provides 4 hours or more of care/day; assists with ADLs)

Exclusion criteria for Supplemental ARM 4 are:

- CG for whom yoga techniques would be detrimental due to physical limitations,
- CG who are enrolled in other Yoga-related clinical trials, or who are currently engaged in regular Yoga activity once per week or more.

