The participant will then be trained on the use of the tablet including the application that will record and transmit their self-entered pain and fatigue symptom scores, the vital sign measuring equipment as well as the video platform for the nurse and self-management program to which they are randomly assigned. The vital sign recording equipment have all been FDA approved and gone through multiple rounds of formal verification. These are also Medical University of South Carolina (MUSC) and South Carolina (SC) Telehealth recommended devices as MUSC is arm of SC Telehealth Alliance. The tablet will be an iPad air 2, which has the communication protocol to connect to all these devices and send encrypted data securely back to servers. In addition, the participants will be given and receive training on a Garmin Vivofit wearable activity tracker that is able to record, steps taken per day, heart rate, distance walked, stairs climbed, and sleep. Garmin Vivofit wearable fitness trackers meet high reliability and validity requirements for parameters such as step counts (Simunek et al., 2016). The training will be conducted via a prerecorded video shown to participants on their tablet at the initial meeting that also explains the program rationale, use of the tablet, activity tracker, and video and app platforms. This video will allow participants access to training at all times in case of issues or questions surrounding the equipment. The PI will contact the participant via their tablet on a weekly basis via the HIPAA compliant telehealth platform Vidyo. Vidyo, a real-time software video communication tool, is HIPAA Compliant with all of the media, signaling, and user login being encrypted to ensure patient privacy and compliance (Vidyo, 2014).²⁸ Each tablet will contain the app "Activate for Life". This app will allow the participant to transmit, via Bluetooth technology their blood pressure and pulse. The app also allows the participant to rate their pain and fatigue scores on a 1-10 scale, document their daily activity and their use of pain medication, and has the ability for the participants to record a voice diary of their daily progress or thoughts. Each participant will receive a blood pressure cuff and will take their blood pressure prior to participating in their PA for the day. The blood pressure and pulse information from the blood pressure monitor will be transferred via Bluetooth to the Activate For Life app on the participants iPad. Once the app has received the data, it will automatically upload the information to the server at MUSC and will be available to be reviewed by the research team. The app will also allow for the participants to input their pain and fatigue scores which will be utilized to monitor pain scores on a daily basis. The vital signs and pain scores will allow for individualizing of the physical activity program to increase or decrease activity based on worsening, improving, or stability of participant's pain as measured by the pain score or through prolonged elevations in blood pressure or pulse. Weekly telehealth visits will allow for delivery of each conditions intervention components, review of pain and/or fatigue, VS, and sleep data. These data will be assessed by the PI and discussed during the weekly telehealth visits with the participants. The burden of self-monitoring and data entry will be captured during feasibility assessments. Saliva samples will be collected from all groups at the beginning and end of the sessions on week 1 and 12 to measure salivary biomarkers including cortisol, and 1,5-AG. Feasibility

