12.0 Data Management

Sample Size Determination. This feasibility study will recruit 30 participants under ARMS 1, 2, and 3. Thirty participants should allow for recruitment of 10 participants from at least 3 different Humanities sites to avoid cross-contamination of study groups. 20 participants will be recruited under the Supplemental ARM AIM 4 to allow for outcome size effect determinations.

Data analysis plan. Measures of feasibility including recruitment and reach, fidelity and adherence, formal satisfaction, and drop-out proportions will be evaluated. Then 95% confidence intervals for proportions will be used to estimate dichotomous outcomes (e.g., the proportion of subjects who: agree to participate out of the number that are approached, the proportion who complete the intervention, the proportion who report satisfaction with the intervention, and the proportion who exit the study prematurely [drop out]). Further, the participants' reasons for drop out, and problems/issues encountered with the intervention will be described via frequency distributions. For continuous measures (e.g. satisfaction scores), frequency distributions and the median and mean responses (with 95% confidence intervals) will be obtained. Formative and summative qualitative interviews will be recorded with the residents and students, transcribed, analyzed with discourse analysis³⁶ and interpreted to evaluate the program design and effectiveness and to make necessary changes based on feedback. Univariate descriptive statistics and frequency distributions will be calculated as appropriate for all variables. Demographic variables obtained at baseline will be described via measures of central tendency (mean, median), variability and frequency distributions as appropriate. Additionally, characteristics for those who were eligible for study versus those who were not eligible and for those who adhered to the study protocol (study completers) versus those who did not adhere (non-adherers and drop-outs) will be compared to better describe the population for this study.

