4) Examples of Potential Reportable Adverse Events: In accordance with MUSC IRB Adverse Event Reporting Policy, an AE is reportable if it meets all of the following criteria: 1) is unexpected 2) is related and/or possibly related, and 3) is serious and/or suggests that the research places subjects or others at a greater risk of physical or psychological harm than was previously known or recognized. Additionally, per MUSC's policy all participant deaths, protocol deviations, complaints about the research, and breaches of confidentiality are reportable events. An example of an AE would be new onset chest pain and discomfort (symptom) that could potentially be associated with increased physical activity. The participant's parent reported he/she recently ran out of his/her medication. The steps to be taken include withdrawing the subject from the study and inviting him or her to restart the study after symptoms subside. An example of an SAE would be the death of a participant from acute chest syndrome or stroke, which although would be viewed as unexpected and unrelated to the intervention is nonetheless a reportable serious event. No further steps would be taken except to review, grade and report the event. An example of an unanticipated problem would be the participant trips and falls while participating in the exercise program. The steps in this case would be to report the event as per the IRB and NINR policy, and to discuss appropriate actions regarding whether the participant should remain in the study with the ISM and SMC. These events and problems will be reported in accordance with the IRB and NIH/NINR policy as noted in Section C.3.

SECTION D. Multi-site Monitoring and Compliance

This is not a multi-site study.

SECTION E. Assessment of External Factors

The PI will conduct a semi-annual assessment of external factors through a review of literature related to new developments in the areas of self-management and symptom management of chronic pain and/or fatigue, symptom reporting and other approaches that may have an impact on the safety of participants or on the ethics of the study.

SECTION F. Interim Analysis

This study aims to test the feasibility of a multi-component, technology-based intervention to promote self-management and symptom management of chronic pain and fatigue among low-income older adults. To our knowledge, there are no similar interventions specifically designed for this patient

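### Two adverse-event examples take the participant out of the study and invite a restart, instead of stopping the exercise and keeping outcome follow-up on the original record.

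*Protocol*

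**What the plan says.** Section 13.0 of the protocol has two data and safety monitoring plans. In each, Section C.4 gives examples of potentially reportable events.

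- **Arms 1-3, new chest pain:** "The steps to be taken include withdrawing the subject from the study and inviting him or her to restart the study after symptoms subside".
- **Arm 4, neck strain during yoga breathing:** the steps are to "withdraw the participant from the study and invite him or her to restart the study after the strain has resolved".
- **Arms 1-3, a fall during exercise:** report it, and "discuss appropriate actions regarding whether the participant should remain in the study with the ISM and SMC".
- **Arm 4, dizziness:** withdrawal is one option among several, depending on severity.

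Section 4.0, which covers all arms, lists among the ways a participant's study can end "PI termination due to failure to adhere to the protocol, loss of contact with the patient, and/or unexpected adverse events". Section 10.0 (Arms 1-3) has daily symptom and vital-sign data feed the "individualizing of the physical activity program to increase or decrease activity".

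Reported adverse events are tracked to resolution in Arms 1-3 (Section 13.0, B.1) and followed up by the Project Director in Arm 4. That is follow-up of the event. No text keeps the week-12 visit, or the 3-month visit in Arms 1-3, for someone withdrawn after an event. Neither document says which ID, baseline or visit dates apply on return. Section 12.0 and the SAP both report premature exit as the drop-out proportion, and the SAP fills missing data by mean substitution.

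**The concern.** The wording takes the person out of the study, not only out of the exercise. Outcome data would then be lost selectively, on people whom the intervention may have harmed. Under the SAP those values would be replaced by an average, which could hide a worsening.

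Two stated aims are touched. Aim 3 looks for within-subject improvement over baseline, so it matters which record and which visits are used for someone who leaves and returns. Attrition has a feasibility hypothesis: below 25% in Aim 2, and at most 25% for Arm 4 in Section 3.0.

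**Working it through.** The plan gives no figure for such events or for restarts, so there is none to reproduce. The check sets the texts side by side and then works out what one person is worth.

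**1. Is withdrawal the general response?** No. Of the four examples above, two withdraw and invite a restart, one refers the question to the safety monitor and committee, and one makes withdrawal depend on severity. The chest-pain example also refers to a participant whose "parent reported he/she recently ran out of his/her medication", although Arms 1-3 enrol "Males and females 60 years of age and older". It was probably carried over from another study.

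**2. Does other text keep the outcome visits?** No. The safety text follows the event, Section 4.0 allows termination by the investigator, and Section 10.0 only adjusts the exercise dose. That adjustment is driven by pain scores and prolonged rises in blood pressure or pulse in Arms 1-3. It does not address new chest pain and does not cover Arm 4.

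**3. How is the withdrawal counted?** As a premature exit, by the ordinary reading of Section 4.0, Section 12.0 and the SAP. The gap is what happens to the data of someone who returns.

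**4. What is one person worth?** Planned numbers are 30 (Arms 1-3) and 20 (Arm 4), from Section 6.0.

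- 1/30 = 3.3 points; 1/20 = 5.0 points.

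| Exits | Proportion | Exact 95% CI | Hypothesis met? |
|---|---|---|---|
| 7 of 30 | 23.3% | 9.9-42.3% | yes (below 25%) |
| 8 of 30 | 26.7% | 12.3-45.9% | no |
| 5 of 20 | 25.0% | 8.7-49.1% | yes (at most 25%) |
| 6 of 20 | 30.0% | 11.9-54.3% | no |

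One person matters to the hypothesis only at those margins, and the intervals on either side overlap almost entirely.

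**5. How likely is it that a restarter changes that reading?** Assume true attrition p of 10-30%, that 10-20% of exits are adverse events of this kind, and that 5-10% of those people restart and complete. None of these figures is in the documents. The share of all exits that restart is then q = 0.10 × 0.05 = 0.5% to 0.20 × 0.10 = 2%.

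- Expected restarters, n × p × q: 30 × 0.10 × 0.005 = 0.015 to 30 × 0.30 × 0.02 = 0.18 in Arms 1-3; 20 × 0.10 × 0.005 = 0.01 to 20 × 0.30 × 0.02 = 0.12 in Arm 4.
- Chance that leaving restarters out of the exits changes whether the hypothesis is met: F(k; n, p(1 − q)) − F(k; n, p), where F is the binomial distribution function and k is the largest count that meets the hypothesis (7 of 30, 5 of 20). This gives about 0.02-2.6% in Arms 1-3 and 0.03-2.3% in Arm 4. These are upper figures, because step 3 already settles the default count.

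**The case against.** The strongest reply is that no policy exists to criticise. The sentences illustrate what is reported to the IRB, the neighbouring examples leave participation open, and one of the two looks like carried-over text. The chest-pain steps are also introduced as a list that need not be complete. All of this stands, and it limits the weight of the point. Even so, these examples are the only text on restarting, and staff facing such an event would look there.

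A reader might infer that a returning participant gets a second baseline after exposure, or is randomised again, so that the change score shrinks. The documents do not support that. No text prescribes either step, and restarting can simply mean resuming. The size of any loss would depend on how gains accrue after the return. A baseline taken while symptoms were worse could enlarge the change score instead.

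A reader might also infer that the attrition result is seriously exposed. That would require applying a restart rate to every exit, including withdrawn consent and lost contact, whereas the invitation appears only in two adverse-event examples. No text attaches a progression decision to the 25% figure.

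Stopping participation for new chest pain in people aged 60 and over is a defensible caution, so follow-up should not be kept automatically. The fix has to leave room for a safety decision and fit with Section 4.0.

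Finally, the SAP is dated 03/12/2021 and written in the past tense. If enrolment has closed, rewording the examples cannot change the data, and only the reporting part is usable.

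**Conclusion.** The point holds as a minor one. If followed as written, the two examples end outcome follow-up because of an adverse event and leave open which record is analysed on return. Stopping the exercise while keeping follow-up is a better and cheap alternative.

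The expected effect is very small. One person is 3.3 points of 30 or 5 points of 20, and under the assumptions shown fewer than 0.2 restarters are expected in either population. That rests on planned enrolment and on assumed event and restart rates. It says nothing about whether a restart occurred. The drop-out count is not in doubt, and a second baseline is not something the plan calls for.

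**What to change.** Replace the withdraw-and-restart step in both C.4 examples with wording such as:

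> Stop the exercise. Unless consent is withdrawn, or the PI with the ISM/SMC (Arm 4: the SMC Chair) judges continued participation unsafe, the participant stays in follow-up on the original ID, arm, baseline and visit schedule, with outcome assessments done where safe. Resuming exercise is a clinical decision.

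Align Section 4.0, so that termination for an unexpected adverse event means stopping the intervention, with outcome follow-up kept where it is safe and consented. Delete the sentence about the parent.

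If enrolment has closed, report whether anyone restarted, count the first withdrawal once as a premature exit, and analyse the original record.

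The cost is wording in three places and two date fields (exercise stopped, exercise resumed), or one reporting sentence if enrolment has closed. The downside is dose: a paused participant may reach week 12 with less than the full programme. A 2-week pause is 2/12 = 16.7% of that person's dose and a 4-week pause is 4/12 = 33.3%. If gain is proportional to dose (an assumption), this lowers the mean gain by 1.7% or 3.3% in an arm of 10, and by 0.8% or 1.7% among 20.
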